4.3.3 Clinical Laboratory Tests

A laboratory manual will be provided to the sites that specifies the procedures for collection, processing, storage, and shipment of samples, as well as laboratory contact information, specific to this clinical research study.

Clinical laboratory safety tests, including urine pregnancy tests, will be performed in a licensed clinical laboratory. Urine pregnancy test will be conducted at Screening and on [REDACTED] Urine pregnancy tests may be performed at the site using a licensed test (dipstick). Clinically significant (as determined by the investigator) abnormal laboratory results should be repeated as soon as possible (preferably within 24 to 48 hours).

The following clinical laboratory tests will be performed:

4.3.3.1 Serum Chemistry

- Calcium
- Phosphorus
- Chloride
- Potassium
- Sodium
- Bicarbonate
- AST
- ALT
- ALP
- Total bilirubin
- Gamma glutamyl transferase
- Creatinine
- Blood urea nitrogen
- Glucose
- Albumin
- Creatinine kinase

Note: Tests for AST, ALT, ALP, and total bilirubin must be conducted concurrently and assessed concurrently. Please refer to Section 10.5 if a subject shows an AST or ALT $\geq 3 \times$ ULN or total bilirubin $\geq 2 \times$ ULN.

4.3.3.2 Hematology

- White blood cell count with differential (%) and absolutes)
- Red blood cell count
- Hematocrit
- Hemoglobin
- Platelet count
- Mean corpuscular volume
- Mean corpuscular hemoglobin concentration

4.3.3.3 Urinalysis

- Color
- Appearance
- Specific gravity
- pH
- Protein
- Glucose
- Ketones
- Blood
- Leukocyte esterase
- Bilirubin
- Urobilinogen
- Nitrite
- Urine microscopy and urine casts (as required if dipstick at central laboratory is abnormal)

4.3.3.4 Pregnancy Test (Females Only)

- Urine human chorionic gonadotropin (hCG)

4.3.3.5 Lipids for Eligibility at Screening (Fasting for a Minimum of 8 Hours)

- Triglycerides
- LDL-C (by direct measure)
- HDL-C

4.3.3.6 Other Safety Tests (Screening Only)

- Thyroid stimulating hormone
- Follicle stimulating hormone (FSH; females only)
- Hepatitis B surface antigen, Hepatitis C antibody
- HIV-1, -2 antibodies
- Glycated hemoglobin

4.3.3.7 Other Tests:

- [REDACTED]
- TC
- HDL-C
- NonHDL-C
- LDL-C (direct and Friedewald equation)
- Very-low-density lipoprotein cholesterol (VLDL-C)
- Triglycerides
- ApoA1
- ApoB

[REDACTED]

[REDACTED]

[REDACTED]

4.3.4 Pharmacokinetic Evaluation and Methods

Blood samples will be collected to evaluate PK of MEDI5884 in serum (see Section 4.2.2 for collection time points). The PK of MEDI5884 in serum will be measured utilizing a validated immunoassay method. Specific procedures for sample collection, processing, storage, and shipment can be found in a separate laboratory manual provided to the sites.

4.3.5 Immunogenicity Evaluation and Methods

Blood samples will be collected to evaluate ADA response to MEDI5884 (see Section 4.2.2 for collection time points). These evaluations will be performed utilizing a validated immunoassay method. Specific procedures for sample collection, processing, storage, and shipment can be found in a separate laboratory manual provided to the site.

If a subject's final scheduled immunogenicity sample is > Baseline, the subject will return to the study site as described in Section 4.2.3.

Serum samples collected for ADA should be stored for 2 years after marketing approval, and they may be utilized for further characterization of the antibody response.

4.3.6 Pharmacodynamic Evaluation and Methods

Blood samples will be collected to evaluate the PD response to MEDI5884 (see Section 4.2.2 for collection time points). PD endpoints may include HDL-C, TC, nonHDL-C, LDL-C (direct and Friedewald equation), VLDL-C, triglycerides, [REDACTED]

[REDACTED] HDL-C, TC, nonHDL-C, LDL-C, VLDL-C, triglycerides, [REDACTED] will be measured by using a validated assay. [REDACTED], apoB, and apoA1 will be measured by using a qualified immunoassay method. [REDACTED]

Specific procedures for sample collection, processing, storage, and shipment can be found in a separate laboratory manual provided to the site.

4.3.7 Estimate of Volume of Blood to Be Collected

The estimated volume of blood to be collected per subject is presented in [Table 4.3.7-1](#). Additional blood samples may be collected at the discretion of the investigator in the event of abnormal laboratory findings or an AE.

Table 4.3.7-1 Estimate of Blood Volume to be Collected

Visit Day	Estimated Blood Volume (mL)
[REDACTED]	15.0
[REDACTED]	102.0
[REDACTED]	8.5
[REDACTED]	10.5
[REDACTED]	8.5
[REDACTED]	8.5
[REDACTED]	8.5
[REDACTED]	32.5
[REDACTED]	3.0
[REDACTED]	32.5
[REDACTED]	8.5
[REDACTED]	8.5
[REDACTED]	8.5
[REDACTED]	40.5
[REDACTED]	10.5
[REDACTED]	32.5
[REDACTED]	3.0
[REDACTED]	3.0
[REDACTED]	6.0
Total	350.5

^a [REDACTED] blood draws will occur only for subjects who require additional follow-up (See Section [4.2.3](#))

4.4 Study Suspension or Termination

The sponsor reserves the right to temporarily suspend or permanently terminate this study at any time. The reasons for temporarily suspending or permanently terminating the study may include but are not limited to the following:

1. The incidence or severity of AEs in this or other studies indicates a potential health hazard to subjects
2. Anaphylaxis in any subject assessed as related to MEDI5884
3. Subject enrollment is unsatisfactory
4. Noncompliance that might significantly jeopardize the validity or integrity of the study
5. Sponsor decision to terminate development of the investigational product for this indication

If MedImmune determines that temporary suspension or permanent termination of the study is required, MedImmune will discuss the reasons for taking such action with all participating investigators (or head of the medical institution, where applicable). When feasible, MedImmune will provide advance notice to all participating investigators (or head of the medical institution, where applicable) of the impending action.

If the study is suspended or terminated for safety reasons, MedImmune will promptly inform all investigators, heads of the medical institutions (where applicable), and/or institutions conducting the study. MedImmune will also promptly inform the relevant regulatory authorities of the suspension/termination along with the reasons for such action. Where required by applicable regulations, the investigator or head of the medical institution must inform the Institutional Review Board (IRB) promptly and provide the reason(s) for the suspension/termination. If the study is suspended for safety reasons and it is deemed appropriate by the sponsor to resume the study, approval from the relevant regulatory authorities (and IRBs when applicable) will be obtained prior to resuming the study.

4.5 Investigational Products

4.5.1 Identity of Investigational Product(s)

4.5.1.1 Investigational Product Handling

4.5.1.2 Investigational Product Inspection

4.5.1.3 Dose Preparation Steps

4.5.1.4 MEDI5884 Reconstitution Procedure

Calculations

1. [REDACTED]

3.

4.5.1.6 Subcutaneous Dose Preparation:

1.

3

4.5.1.7 Treatment Administration

[REDACTED]

4.5.1.8 Monitoring of Dose Administration

[REDACTED]

[REDACTED]

[REDACTED]

[REDACTED]

[REDACTED]

4.5.2 Additional Study Medications

[REDACTED]

[REDACTED]

[REDACTED]

[REDACTED]

[REDACTED]

4.5.3 Labeling

[REDACTED]

[REDACTED]

4.5.4 Storage

[REDACTED]

[REDACTED]

4.5.5 Treatment Compliance

[REDACTED]

[REDACTED]

4.5.6 Accountability

[REDACTED]

[REDACTED]

[REDACTED]

[REDACTED]

4.6 Treatment Assignment and Blinding

4.6.1 Methods for Assigning Treatment Groups

An IXRS will be used for randomization to a treatment group and assignment of blinded investigational product. A subject is considered randomized into the study when the investigator notifies the IXRS that the subject meets eligibility criteria and the IXRS provides the assignment of blinded investigational product kit numbers to the subject.

[REDACTED]

[REDACTED]

[REDACTED]

Investigational product (MEDI5884 or placebo) must be administered the same day the investigational product is assigned. If there is a delay in the administration of investigational product such that it will not be administered within the specified timeframe, the study monitor must be notified immediately

4.6.2 Methods to Ensure Blinding

This is a double-blind study in which MEDI5884 and placebo are visually distinguishable until SC doses are prepared. Neither the subject nor any of the investigator or sponsor staff who are involved in the treatment or clinical evaluation of the subjects will be aware of the treatment received (ICH E9).

In order to maintain the blind, an unblinded pharmacist will be responsible for dose preparation. Volume matched placebo injections will be prepared as per [Table 4.5.1.6-1](#). Once prepared, MEDI5884 and placebo are indistinguishable. A blinded qualified designee will administer investigational product to subjects via SC injection.

The investigational product manager/unblinded study personnel must ensure that only the unblinded team members (ie, study pharmacist) have access to the areas of the pharmacy where the investigational product is being prepared. An independent investigational product monitor will also be unblinded to perform investigational product accountability. In the event that treatment allocation for a subject becomes known to the investigator or other study personnel involved in the management of the study subject, the sponsor must be notified immediately. If the identity of a treatment needs to be unblinded for a subject in order to treat that individual subject for an AE, the investigator must notify the sponsor immediately. The site will maintain a written plan detailing which staff members are blinded/unblinded and the process of investigational product administration used to maintain the blind.

4.6.2.1 Unblinding in the Event of a Medical Emergency

In the event of a medical emergency, the investigator may unblind an individual subject's investigational product allocation. Instructions for unblinding an individual subject's investigational product allocation are contained in the IXRS manual. In general, unblinding should only occur if management of the medical emergency would be different based on the subject having received investigational product. In most cases, the management of a medical emergency would be the same whether the investigational product was received by the subject or not. In such cases, the identity of the investigational product should remain blinded.

MedImmune retains the right to unblind the treatment allocation for serious adverse events (SAEs) that are unexpected and are suspected to be causally related to an investigational product and that potentially require expedited reporting to regulatory authorities.

4.6.2.2 Unblinding for the Interim Analysis

MedImmune personnel will be unblinded at the interim analysis; study subjects, the investigator, and site staff who are involved in the treatment or clinical evaluation of subjects will remain blinded until the end of study.

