4.6.2.3 Unblinding for Pharmacokinetic and Immunogenicity Analysis

A small number of clinical bioanalytical personnel, who will not be involved in the treatment or clinical evaluation of subjects, will be unblinded to subject treatment allocation to analyze PK and immunogenicity samples. Local standard operating procedures will govern maintenance of the blind and information on treatment allocation will not be communicated outside of these personnel.

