10.5.1 Introduction

This appendix describes the process to be followed to identify and appropriately report cases of Hy's Law. It is not intended to be a comprehensive guide to the management of elevated liver biochemistries.

During the course of the study, the investigator will remain vigilant for increases in liver biochemistry. The investigator is responsible for determining whether a subject meets potential Hy's Law criteria at any point during the study.

The investigator participates, together with MedImmune clinical project representatives, in review and assessment of cases meeting potential Hy's Law criteria to agree whether Hy's Law criteria are met. Hy's Law criteria are met if there is no alternative explanation for the elevations in liver biochemistry other than drug-induced liver injury (DILI) caused by the investigational product.

The investigator is responsible for recording data pertaining to potential Hy's Law/Hy's Law cases and for reporting AEs and SAEs according to the outcome of the review and assessment in line with standard safety reporting processes.

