10.5.3 Identification of Potential Hy's Law Cases

In order to identify cases of potential Hy's Law, it is important to perform a comprehensive review of laboratory data for any subject who meets any of the following identification criteria in isolation or in combination:

- ALT $\geq 3 \times$ ULN
- AST $\geq 3 \times$ ULN
- TBL $\geq 2 \times$ ULN

In cases where a subject may meet any of the abnormal laboratory identification criteria, in isolation or in combination, the central laboratory will immediately send an alert to the investigator (also sent to sponsor study representative).

The investigator will also remain vigilant for any local laboratory reports where the identification criteria are met, where this is the case the investigator will:

- Notify the sponsor study representative
- Request a repeat of the test (new blood draw) by the central laboratory
- Complete the appropriate unscheduled laboratory case report form (CRF) module(s) with the original local laboratory test result

When the identification criteria are met from central or local laboratory results the investigator will without delay:

- Determine whether the subject meets potential Hy's Law criteria (see Section 10.5.2) by reviewing laboratory reports from all previous visits (including both central and local laboratory results)

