10.5.5 Review and Assessment of Potential Hy's Law Cases

The instructions in this section should be followed for all cases where potential Hy's Law criteria are met.

No later than 3 weeks after the biochemistry abnormality was initially detected, the medical monitor will contact the investigator in order to review available data and agree on whether there is an alternative explanation for meeting potential Hy's Law criteria other than DILI caused by the investigational product. The medical monitor and Global Safety Physician will also be involved in this review together with other subject matter experts as appropriate.

According to the outcome of the review and assessment, the investigator will follow the instructions below.

If there is an agreed alternative explanation for the ALT or AST and TBL elevations, a determination of whether the alternative explanation is an AE will be made and subsequently whether the AE meets the criteria for a SAE:

- If the alternative explanation is **not** an AE, record the alternative explanation on the appropriate CRF
- If the alternative explanation is an AE/SAE, record the AE /SAE in the CRF accordingly and follow the sponsor's standard processes

If it is agreed that there is **no** explanation that would explain the ALT or AST and TBL elevations other than the investigational product:

- Report an SAE (report term ‘Hy’s Law’) according to the sponsor’s standard processes.
 - The ‘Medically Important’ serious criterion should be used if no other serious criteria apply
 - As there is no alternative explanation for the Hy’s Law case, a causality assessment of ‘related’ should be assigned

If, there is an unavoidable delay of over 3 weeks in obtaining the information necessary to assess whether or not the case meets the criteria for Hy’s Law, then it is assumed that there is no alternative explanation until such time as an informed decision can be made:

- Report an SAE (report term ‘Potential Hy’s Law’) applying serious criteria and causality assessment as per above
- Continue follow-up and review according to agreed plan. Once the necessary supplementary information is obtained, repeat the review and assessment to determine whether Hy’s Law criteria are met. Update the SAE report according to the outcome of the review

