2.3 Treatment Assignment and Blinding

An (Interactive voice/web response system) IXRS will be used for randomization to a treatment group and assignment of blinded investigational product. A subject is considered randomized into the study when the investigator notifies the IXRS that the subject meets eligibility criteria and the IXRS provides the assignment of blinded investigational product kit numbers to the subject.

Subjects will be randomized in a [REDACTED] ratio to receive MEDI5884 ([REDACTED] [REDACTED]) or placebo (volume matched to [REDACTED] MEDI5884).

[figure not shown]
This is a double-blind study in which MEDI5884 and placebo are visually distinguishable until SC doses are prepared. Neither the subject nor any of the investigator or sponsor staff

who are involved in the treatment or clinical evaluation of the subjects will be aware of the treatment received (ICH E9).

In order to maintain the blind, an unblinded pharmacist will be responsible for dose preparation including preparation of volume matched placebo injections.

Once prepared, MEDI5884 and placebo are indistinguishable. A blinded qualified designee will administer investigational product to subjects via SC injection.

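### Does unblinding sponsor personnel at the interim, with no roles named, undermine the safety assessment?

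*Protocol*

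**What the plan says.** The general rule is in Protocol 4.6.2: "Neither the subject nor any of the investigator or sponsor staff who are involved in the treatment or clinical evaluation of the subjects" will know the treatment received. SAP 2.3 repeats it. Neither place mentions the interim.

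Three subsections of 4.6.2 then describe specific unblinding:

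- **4.6.2.1, medical emergency.** The investigator may break the code for a subject. The sponsor also keeps a case-level route: "MedImmune retains the right to unblind the treatment allocation for serious adverse events (SAEs) that are unexpected" and suspected to be caused by the product.
- **4.6.2.2, interim analysis.** "MedImmune personnel will be unblinded at the interim analysis; study subjects, the investigator, and site staff"; the sentence ends by keeping those three groups blinded to the end of study. SAP 4 uses the same sentence.
- **4.6.2.3, PK and immunogenicity assays.** A few bioanalytical staff with no part in clinical evaluation are unblinded, and "information on treatment allocation will not be communicated outside of these personnel".

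Protocol 4.8.7 gives only the timing of the interim, with the visit redacted.

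Appendix 5 (10.5.1) has the investigator act "together with MedImmune clinical project representatives, in review and assessment of cases meeting potential" Hy's Law criteria. Section 10.5.5 adds: "The medical monitor and Global Safety Physician will also be involved in this review together with other subject matter experts as appropriate". SAP 3.7.2 lists Hy's Law as the only adverse event of special interest.

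**The concern.** Read in isolation, 4.6.2.2 opens the code to an unspecified set of sponsor staff while adverse events are still being collected (Protocol 5.4.1 runs collection to the end of study). It gives no role, no number, no level of unblinding and no rule on passing information on. Redaction does not explain this, since only the visit label is hidden in 4.8.7 and SAP 4. The next subsection supplies most of what is missing for a much smaller group, so the omission stands out.

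The general rule also protects sponsor staff in clinical evaluation, and nothing says whether that protection survives the interim. Safety is the primary objective. Hy's Law status depends on judging that nothing but the product explains the liver values, and sponsor staff share in that judgement. If they knew the arm, the assessment of the one special-interest event could be influenced by it.

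**Working it through.** No calculation applies, so the check compares the passages under each possible reading.

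**1. Scope of the exception.** The general rule names subject, investigator and sponsor staff as blinded. The interim sentence reuses the same qualifier about involvement in treatment or clinical evaluation, but attaches it to site staff in place of sponsor staff. It stands under 4.6.2 beside two other exceptions and under a heading about unblinding. There are two ways to read it:

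- *Deliberate exception.* Sponsor staff may be unblinded at the interim; subjects, investigators and sites may not. The text then states its outer limits, though not the roles.
- *General rule still binds.* Sponsor staff in clinical evaluation stay blinded and only others are unblinded. The Hy's Law exposure then disappears.

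The first reading is the more natural. Neither makes the documents contradict each other.

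**2. What must happen for harm under the first reading.** All of the following are needed:

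1. A subject meets the potential Hy's Law criteria (no rate is given).
2. The case is assessed, or reassessed, after the interim.
3. A sponsor reviewer holds subject-level codes. Section 4.6.2.2 does not say subject level; 4.6.2.3 does.
4. Knowing the arm alters that reviewer's opinion.
5. The blinded investigator agrees to the altered opinion (10.5.1, 10.5.5).

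Of the reviewers, only the clinical project representatives are identified as MedImmune staff. The documents do not say who employs the medical monitor or the Global Safety Physician.

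**3. What does not depend on the sponsor's opinion.**

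- Flagging follows fixed multiples of the upper limit of normal, and the central laboratory alerts the investigator and the sponsor together (10.5.3).
- Severity and relationship of adverse events are assessed by the investigator (Protocol 5.4, 10.3.1.4 and 10.3.1.5).
- If the information is unavoidably delayed beyond 3 weeks, the case is reported as a related SAE in the meantime (10.5.5).
- Serum chemistry is summarised by arm at scheduled visits with shift tables (SAP 3.7.4), and data are listed by treatment group and subject (SAP 3.1). The shift tables show only low, normal or high, but the descriptive statistics include the maximum.
- Safety is descriptive, with no formal comparison (SAP 3.7). No stopping or adaptation rule accompanies the interim, so there is no type I error cost.

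**4. Can the opportunity be bounded?** The schedule in Protocol 4.2.2 shows 5 marks for serum chemistry, one of them at V2, leaving 5 − 1 = 4 scheduled panels after that visit. This does not bound the exposure:

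- The interim visit is redacted, so the number of panels after it is unknown.
- A panel drawn before the interim can be judged after it, because the review contact may come up to 3 weeks after detection and delayed cases are reviewed again.
- Unscheduled visits, repeat tests and local laboratory results can also raise a case.

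The size therefore stays unquantified.

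**The case for a change.** The strongest case for acting is that the protocol already knows how to do this. Section 4.6.2.3 limits number, function and communication in a couple of sentences, and the same could be written for the interim. Hy's Law is a consequential label, safety is the primary objective, and blinding of sites to the end of study implies that follow-up continues after the interim. The written blinding plan in 4.6.2 belongs to the site and does not cover the sponsor.

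All of that is accurate, and the missing detail is real. It does not carry the point, for three reasons.

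- The documents show that a reviewer could know the arm, not that one will, and the safeguards above limit what that knowledge could change.
- Barring sponsor clinical staff from subject-level data in a Phase 2a study is a trade-off. Protocol 1.5 says the data are to support dose selection for later studies. The documents do not show how the sponsor team is staffed, so the cost of splitting it is unknown. If the edit counted as substantial, Protocol 7.4 would require an amendment and IRB approval, with about 25 sites planned.
- The protection would be partial. Agreed or delayed Hy's Law cases are reported as related SAEs, and 4.6.2.1 already allows the sponsor to unblind such an event if it is also unexpected. Only the judgement made before that report would be shielded.

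Timing also weakens the benefit. The Amendment 4 entry of 29 May 2018 records that dosing was complete, so from then only follow-up remained. Whether the interim was still ahead is not stated.

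**Conclusion.** No change to the plan follows. The interim unblinding is disclosed in both documents, says which groups remain blinded, and is best read as an intended exception to the general rule. What it lacks is operational detail: the sponsor functions, the level of unblinding and a rule on communication. Whether sponsor Hy's Law reviewers should see the codes is a design choice with an unknown staffing cost, not an error.

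Followed as written, the conclusions remain sound. The possible effect is confined to sponsor input on individual Hy's Law cases assessed after the interim. It is probably small and cannot be quantified from the documents. No bias to the apoB or HDL-C comparisons is identified.

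This rests on three conditions stated in the documents: investigators and sites stay blinded to the end of study, the investigator's agreement is needed for Hy's Law status, and safety results are descriptive. It also assumes that no interim decision rule lies behind the redactions; the visible interim text shows none.
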